| | 
from the date of signed informed consent (enrollment) until end of study, which includes withdrawal of consent, loss to follow-up, death, or study completion. Continuation in the study is not contingent on continuation of Valchlor.
 
Patients currently enrolled and ongoing or newly enrolled will be offered to participate in the 24-month study of this protocol Amendment 1. Patients who enrolled under the original protocol (prior to Amendment 1) and are still ongoing in the study will be re-consented and to follow data collection specified in Table 1 of this protocol for a total of 24 months from original consent date. Patients who enrolled and have completed 1 year of the study under the original protocol will not be re-consented under Amendment 1.
 |
| 
POPULATION (SETTING AND STUDY POPULATION)
 | 
This study will enroll approximately 300 consecutive patients diagnosed with MF-CTCL and being treated with Valchlor, regardless of other MF-CTCL therapies received before or at enrollment. Patients will be enrolled from up to 50 participating centers/clinics in university-affiliated or community hospitals in the US. The participation of physicians and patients in the study is on a voluntary basis.
 
Inclusion criteria:
 
 • All adult patients (≥ 18 years of age) diagnosed with MF-CTCL and being treated with Valchlor. This includes patients newly initiating Valchlor OR patients continuing treatment with Valchlor: 
 ○ Patients newly initiating Valchlor are patients who have their first office visit after having initiated Valchlor. ○ Patients continuing treatment with Valchlor includes patients who are actively taking Valchlor on the day of enrollment. ○ Signed patient informed consent. 
Exclusion criteria:
 
 • None |
| 
VARIABLES
 | 
The variables of interest for this study includes clinical characteristics, treatment patterns, clinical status, as assessed by the physician (including the methods used in practice to assess clinical status), MF-CTCL-related healthcare utilization, as assessed by the physician (hospitalizations and emergency room visits), AEs and
 |

| | |
|--|---|

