5 RESEARCH METHODS

5.1 Study design

This is a multi-center, prospective, observational study of MF-CTCL patients who have newly initiated Valchlor or who are continuing treatment with Valchlor.

Patients will be followed by their physician according to routine clinical practice. With the exception of protocol-required patient-completed questionnaires, there are no specific or mandated clinical assessments to be performed, and patients will not receive experimental intervention or treatment as a consequence of their participation in this study. The study protocol will not mandate any specific schedule of visits. Patients will undergo clinical assessments and receive standard medical care as determined by the patient's physician in a real-world setting.

Patients will be followed prospectively for a maximum of 2 years from the date of signed informed consent until end of study (EOS), which includes withdrawal of consent, loss to follow-up, death, or study completion. Continuation in the study is not contingent on continuation of Valchlor.

The study will end after all enrolled patients have been followed for 2 years, or discontinued from the study for any reason.

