The by-time analyses for each visit will provide supportive clinical and statistical mechlorethamine response data over the whole treatment period, before and after the 12 month results. Patient visits were variable throughout the study and no defined patient visits were required in PROVe. Given this construct, the By-Visit analyses of % BSA data, Pruritis VAS, Skin-Dex 29, and the MF/SS CTCL QOL instrument will be constructed from the respective change from baseline that occurred closest to each of the following timepoints 1, 3, 6, 9, 12, 15, 18, 21 and 24 months, and will include data that falls within  $\pm 45$  days of each designated timepoint.

Other secondary endpoints include:

- Overall Response Rate 2 (ORR2) Percent of patients with  $\geq 50\%$  reduction from baseline in % Body Surface Area of disease for at least two consecutive visits.
- Overall Response Rate 4 (ORR4) Percent of patients with  $\geq 50\%$  reduction from baseline in % Body Surface Area of disease for at least four consecutive visits.
- Time to Next Treatment (TTNT). TTNT is defined as the median number of days an individual patient stayed on a treatment before starting a new treatment or adding on an additional treatment.
- Rates of on Study Hospitalization
- Pruritis VAS
- SkinDex-29

- MF/SS CTCL – QOL Instrument

For each endpoint, separate analyses will be done for patients contributing data with IA and IB staging, all staged patients, and all patients regardless of staging. As PROVe is an observational study, an Intent-to-Treat (ITT) population analysis is not applicable. There are no cases where an intention to treat was prevented and therefore no potential for a selection bias in the analyses prespecified in this SAP. This results in a total of 51 analysis types as shown in the Figure 1 below.

Figure 1: Analysis Populations for the PROVe Study

	Patients Contributing Data			Totals:
	IA and IB Staging	All Staged	All Patients with and without Staging	
Primary Endpoint	1	1	1	3
9 By-Time Analyses	9	9	9	27
7 Other Secondary Endpoints	7	7	7	21
			Overall Total:	51

These analyses will be applied to following four (4) analysis populations:

1. Valchlor + corticosteroids + possibly another treatment (primary) (V+C+other)
2. Valchlor + phototherapy + possibly another treatment (V+P+other)
3. Valchlor + oral bexarotene + possibly another treatment (V+B+other)
4. Valchlor + any other treatment (V+other)

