## ASSESSMENT SCHEDULE

Demographics, medical history, current and historical MF-CTCL treatments, clinical status by physician, clinical status assessments, the Visual Analogue Scale (VAS) for pruritus, the Skindex-29, and ongoing adverse events (AEs) and serious adverse events (SAEs) related to Valchlor are collected at the enrollment visit, per routine clinic visits. Any data that is not collected at enrollment or present in the historical patient information will be indicated as not assessed, not applicable or not done, as appropriate. In addition, to appropriately construct change from baseline analyses all baseline data must be verified as such. For example, if a % BSA score is provided at enrollment, it may not represent a baseline disease score if a subject was already using mechlorethamine prior to the collection of that score. The same handling should apply to the PRO questionnaires.

Change in TNMB classification, change in medical history, change in medications with Valchlor and other MF-CTCL treatments, HCU, clinical status by physician, clinical status assessments, VAS for pruritus, the Skindex-29, reports of secondary exposure, and all AEs and SAEs related and unrelated during Valchlor use and >30 days after Valchlor discontinued are collected at follow-up visits during the observation period, as recorded during the routine clinic visit. These visits occur at the physician's discretion (i.e., they are not scheduled per protocol); consequently, the number of follow-up visits will vary across patients. Additionally, the data collected during the visits will be dependent upon routine clinic practice, and thus not all data may be available.

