Extracorporeal photopheresis	x	x.x%	x.x%
HDAC inhibitors, Romidepsin (Istodax)	x	x.x%	x.x%
HDAC inhibitors, Vorinostat (Zolinza)	x	x.x%	x.x%
Interferon, Interferon-alpha (Intron-A, others)	x	x.x%	x.x%
Other systemic	x	x.x%	x.x%
Retinoids, systemic	x		
Retinoids, systemic, Acitretin (Soriatane)	x	x.x%	x.x%
Retinoids, systemic, Bexarotene (Targretin)	x	x.x%	x.x%
Missing	x	x.x%	x.x%

Run Date:  
ddMMMyyyy  
Date of data extraction: ddMMMyyyy

Helsinn Therapeutics (US), Inc.,  
 Protocol AC-079A501 (PROVe)

Table 13. Ongoing Systemic Therapies N=X

Systemic therapy type Class/Type	Frequency count	% of systemic therapy records (n=xx)	% of all "Other MF- CTCL treatment" records (n=xx)
Chemotherapy, systemic,	x	x	x
Chemotherapy, systemic, Methotrexate, oral (Trexall, others)	x	x.x%	x.x%
Chemotherapy, systemic, Pralatrexate (Folotyn)	x	x.x%	x.x%
Extracorporeal photopheresis	x	x.x%	x.x%
HDAC inhibitors, Romidepsin (Istodax)	x	x.x%	x.x%
HDAC inhibitors, Vorinostat (Zolinza)	x	x.x%	x.x%
Interferon, Interferon-alpha (Intron-A, others)	x	x.x%	x.x%
Other systemic	x	x.x%	x.x%
Retinoids, systemic	x	x.x%	x.x%
Retinoids, systemic, Acitretin (Soriatane)	x	x.x%	x.x%
Retinoids, systemic, Bexarotene (Targretin)	x	x.x%	x.x%
Missing	x	x.x%	x.x%

Run Date:

ddMMMyyyy

Date of data extraction: ddMMMyyyy

Helsinn Therapeutics (US), Inc.,  
 Protocol AC-079A501 (PROVe)

Table 14. TNMB Counts At Ongoing Visits

Patient Count N=X		
All Ongoing Visits	Stage (TNMB classification):	Patient Visits n (%)
Ongoing Visits 1 N=X	N/A	x (xx.xx)
	IA	x (xx.xx)
	IB	x (xx.xx)
	IIB	x (xx.xx)
	IVA1	x (xx.xx)
Ongoing Visits 2 n=X	...	x (xx.xx)
Ongoing Visits 3 n=X	...	x (xx.xx)
Ongoing Visits 4 n=X		
Ongoing Visits 5 n=X		
Ongoing Visits 6 n=X		x (xx.xx)
	...	x (xx.xx)
Ongoing Visits 7 n=X		
Ongoing Visits 8 n=X		
Ongoing Visits 9 n=X		
Ongoing Visits 10 n=X		
Ongoing Visits 11 n=X		
Ongoing Visits 12 n=X		
Ongoing Visits >12 n=X		

Run Date: ddMMMyyyy  
 Date of Data Extraction: ddMMMyyyy

Helsinn Therapeutics (US), Inc.,  
 Protocol AC-079A501 (PROVe)  
 Table15. Disease Progression

Baseline	Status at Last Ongoing Visit (N=X)							
	IA	IB	IIA	IIB	IIIA	IIIB	IVA1	Missing
IA	Xx (%)	Xx (%)	Xx (%)	Xx (%)	Xx (%)	Xx (%)	Xx (%)	Xx (%)
IB	Xx (%)	Xx (%)	Xx (%)	Xx (%)	Xx (%)	Xx (%)	Xx (%)	Xx (%)
IIA	Xx (%)	Xx (%)	Xx (%)	Xx (%)	Xx (%)	Xx (%)	Xx (%)	Xx (%)
IIB	Xx (%)	Xx (%)	Xx (%)	Xx (%)	Xx (%)	Xx (%)	Xx (%)	Xx (%)
IIIA	Xx (%)	Xx (%)	Xx (%)	Xx (%)	Xx (%)	Xx (%)	Xx (%)	Xx (%)

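### Table 14 shows TNMB stage by visit number in a study without a visit schedule, so its rows share no time scale and the stage mix can shift without any patient changing stage

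*SAP*

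**What the plan says.** In SAP Appendix A, "Table 14. TNMB Counts At Ongoing Visits" has one block per visit number, from 1 to 12 and then "Ongoing Visits >12 n=X". Each block has its own n, the counting unit is "Patient Visits n", and there is no time window.

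Neither document fixes when visits happen. Protocol section 5.1: "The study protocol will not mandate any specific schedule of visits". SAP, Assessment Schedule: "consequently, the number of follow-up visits will vary across patients".

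Follow-up length differs too. The amended protocol follows patients for up to 24 months, but its synopsis states: "Patients who enrolled and have completed 1 year of the study under the original protocol will not be re-consented under Amendment 1". Those patients have 12 months.

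The SAP knows that visit number is a poor index here. Under Analysis Populations it notes: "Patient visits were variable throughout the study and no defined patient visits were required in PROVe". It then moves the by-visit analyses of BSA and the patient questionnaires to months 1, 3, 6, 9, 12, 15, 18, 21 and 24, each ±45 days. TNMB stage is not on that list.

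Two further items matter. The SAP's Table 1 shows that follow-up visits collect TNMB as a change in classification. Table 15 cross-tabulates baseline stage against stage at the last ongoing visit.

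**The concern.** Visit k falls at a different time for each patient, and the patients who reach a high k are selected by how often they are seen, how long they are followed, or both. Reading down Table 14 compares different subsets of patients at unaligned times. Because the unit is patient visits, the >12 row can also count one patient several times.

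At stake is the first objective, which includes describing clinical characteristics during the observation period. A reader who scans the rows as a time course could take a change in who is being counted for a change in disease stage.

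**Working it through.** Table 14 is an empty shell, so there is no plan figure to reproduce. The check is how far the stage mix can move when no stage changes.

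**Step 1: who can reach a late row.** The largest mean interval that reaches visit 12 is 12/12 = 1.0 month with 12-month follow-up and 24/12 = 2.0 months with 24. With quarterly visits a 12-month patient stops at visit 12/3 = 4 and a 24-month patient at visit 24/3 = 8. Late rows therefore need frequent visits, long follow-up, or both.

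**Step 2: inputs.**
- From Protocol section 5.5: about 300 enrolled, and about 200 evaluable patients projected under the 24-month amendment. I take 200/300 = 2/3 followed 24 months and 1/3 followed 12. Using 200/270 evaluable = 74% instead barely changes the results.
- Assumed, because the documents give nothing: 20% advanced stage, and the visit rates in the table below.
- Assumed spread: visit counts are Poisson, either with one rate per stage group or with rates varying between patients (gamma, shape 4, giving negative binomial counts).

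**Step 3: formula.** With X the number of visits, P(reach k) = (2/3)·P(X ≥ k in 2 years) + (1/3)·P(X ≥ k in 1 year). Call this E for early and A for advanced patients. The advanced share at visit k is 0.2A / (0.2A + 0.8E).

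**Step 4: results at visit 12, every stage fixed.**

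| Visits/year, early vs advanced | Spread | E | A | Advanced share | Expected n of 300 |
|---|---|---|---|---|---|
| 3 vs 5 | gamma | 0.0616 | 0.2423 | 49.6% | 29 |
| 3 vs 5 | none | 0.0134 | 0.2040 | 79% | 15 |
| 4 vs 5 | none | 0.0749 | 0.2040 | 40.5% | 30 |
| 4 vs 4 | none | 0.0749 | 0.0749 | 20.0% | 22 |
| 4 vs 3 | gamma | 0.1454 | 0.0616 | 9.6% | 39 |
| 4 vs 3 | none | 0.0749 | 0.0134 | 4.3% | 19 |

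First line worked: 0.2 × 0.2423 = 0.0485; 0.8 × 0.0616 = 0.0493; 0.0485 / 0.0978 = 49.6%. With 74% on 24-month follow-up it is 49.2%.

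With equal rates the advanced share is 20.0% in every row, although the row n still falls from 298 at visit 1 to 115 at visit 8 (no spread). With 3 vs 5 and gamma spread it goes 20.6%, 25.4%, 35.8%, 49.6% at visits 1, 4, 8 and 12.

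**Step 5: follow-up length alone.** With 4 visits a year in both groups, but 50% rather than 67% of advanced patients on 24-month follow-up, the advanced share is 16.4% at visit 8 and 15.8% at visit 12.

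**Step 6: the >12 row.** In a simulation of the 3 vs 5 gamma case, patients who pass visit 12 contribute about 4.4 visits each beyond it.

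**Step 7: does a month index cure it?** Take the 3 vs 5 gamma case and follow-up unrelated to stage. If every patient under observation is counted at the last recorded stage, the advanced share is 20% at each timepoint. If only patients with a visit in a 90-day window count, P(at least one visit) = 1 − (4/(4 + m))⁴ with m = rate × 90/365. This gives 0.493 early and 0.658 advanced, so the share is 0.2 × 0.658 / (0.2 × 0.658 + 0.8 × 0.493) = 25%. The choice of denominator matters as much as the window.

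**The case against.** The strongest reply is that the SAP has a table for progression and it is Table 15, which compares baseline with last stage within patients and is untouched by visit-number selection. That stands. A reader might infer that Table 14 is the only output of stage over time; it is not. Table 15 does not fill the gap, however: the last visit may fall near month 12, near month 24 or earlier, so it gives no stage at a common time.

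A second reply is that the shift is conditional. That also stands. A reader might infer that the advanced percentage must rise with visit number and will look like progression. The documents give no visit rates by stage, equal rates leave the expected mix unchanged, and the reverse pattern lowers it. Nor do late rows hold only 24-month patients: one seen monthly for 12 months reaches visit 12.

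Third, the shell prints an n for each row and names its unit, neither document says the rows are to be read as a trend, and the protocol itself reports other items by visit number (sections 5.7.1, 5.7.3 and 5.7.6). The visible n helps, but it shows that the rows shrink, not who has left. The SAP already dropped visit number for BSA and the questionnaires for this very reason.

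Finally, month windows have limits. They do not remove the 12- versus 24-month selection after month 12. The ±45-day windows at months 1 and 3 overlap, from about day 46 to day 75. Carrying stage forward sits awkwardly with the SAP's missing-data section, which plans no imputation. These stand as conditions on the fix.

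**Conclusion.** The point holds as a limited one. Table 14's rows have no common time, and later rows are selected subsets; both follow from the documents without assumption. Whether the stage mix is distorted, and in which direction, depends on a relation between stage and visit frequency or follow-up length that the documents do not give. Over the assumed visit rates, an unchanging 20% advanced share can appear at visit 12 as anything from about 4% to well over 40%, or as exactly 20%. These are illustrations, not predictions, and they are sensitive to the assumed between-patient spread.

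Tables 14 and 15 together do not describe stage at successive times in the observation period, which is part of the first objective. The issue is minor: a descriptive shell, with no bearing on any primary or secondary endpoint.

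**What to change.** Re-index Table 14 to the SAP's timepoints (months 1, 3, 6, 9, 12, 15, 18, 21, 24), with one stage per patient per timepoint and patients still under observation as denominator.

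- Use the last recorded TNMB, because follow-up records only changes. State that this is an exception to the no-imputation rule in the SAP's missing-data section.
- Show beside each row how many patients had a visit in the window.
- Assign each visit to its nearest timepoint only, so that none counts at both month 1 and month 3.
- Footnote that rows after month 12 hold only patients on 24-month follow-up, and refer to Table 15 for within-patient change.

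The cost is a small amount of programming for one shell and no new data. The price in interpretation is the assumption that no recorded change means unchanged stage. Visit counts by number remain available in Table 1B.

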**Skindex-29 Symptoms**

Baseline Completed [(mean +/- SD) (min, max)]	n= xx.x +/- xx.x (xx,xx)				
Baseline Not Done [(mean +/- SD) (min, max)]					

Follow-Up Completed	n=	n=	n=	n=	n=
Quarter 1 [(mean +/- SD) (min, max)]	xx.x +/- xx.x (xx,xx)				
Quarter 2 [(mean +/- SD) (min, max)]					
Quarter 3 [(mean +/- SD) (min, max)]					
Quarter 4 [(mean +/- SD) (min, max)]					
Follow-Up Not Done [(mean +/- SD) (min, max)]					

**Skindex-29, Functioning**

Baseline Completed [(mean +/- SD) (min, max)]	n= xx.x +/- xx.x (xx,xx)				
Baseline Not Done [(mean +/- SD) (min, max)]					
Follow-Up Completed					
Quarter 1 [(mean +/- SD) (min, max)]	n= xx.x +/- xx.x (xx,xx)				
Quarter 2 [(mean +/- SD) (min, max)]					
Quarter 3 [(mean +/- SD) (min, max)]					
Quarter 4 [(mean +/- SD) (min, max)]					
Follow-Up Not Done [(mean +/- SD) (min, max)]					

- 
- a. Patients can contribute multiple visits to a quarter during the follow-up period. These visits could be categorized as response or non-response for the same patient within a quarter.

Characteristic	V+C+ Other	V+P+ Other	V+OB+ Other	V+ Other
VAS for Pruritus				
Baseline Completed [(mean +/- SD) (min, max)]	n= xx.x +/- xx.x (xx,xx)	n= xx.x +/- xx.x (xx,xx)	n= xx.x +/- xx.x (xx,xx)	n= xx.x +/- xx.x (xx,xx)
Baseline Not Done [(mean +/- SD) (min, max)]				
Follow-Up Completed				
Quarter 1 [(mean +/- SD) (min, max)]	n= xx.x +/- xx.x (xx,xx)	n= xx.x +/- xx.x (xx,xx)	n= xx.x +/- xx.x (xx,xx)	n= xx.x +/- xx.x (xx,xx)
Quarter 2 [(mean +/- SD) (min, max)]				
Quarter 3 [(mean +/- SD) (min, max)]				
Quarter 4 [(mean +/- SD) (min, max)]				
Follow-Up Not Done [(mean +/- SD) (min, max)]				
Skindex-29 Emotions				
Baseline Completed [(mean +/- SD) (min, max)]	n= xx.x +/- xx.x (xx,xx)	n= xx.x +/- xx.x (xx,xx)	n= xx.x +/- xx.x (xx,xx)	n= xx.x +/- xx.x (xx,xx)
Baseline Not Done [(mean +/- SD) (min, max)]				
Follow-Up Completed				
Quarter 1 [(mean +/- SD) (min, max)]	n= xx.x +/- xx.x (xx,xx)	n= xx.x +/- xx.x (xx,xx)	n= xx.x +/- xx.x (xx,xx)	n= xx.x +/- xx.x (xx,xx)
Quarter 2 [(mean +/- SD) (min, max)]				

Quarter 3 [(mean +/- SD) (min, max)]

Quarter 4 [(mean +/- SD) (min, max)]

Follow-Up Not Done [(mean +/- SD) (min, max)]

**Skindex-29 Symptoms**

Baseline Completed [(mean +/- SD) (min, max)]	n= xx.x +/- xx.x (xx,xx)				
Baseline Not Done [(mean +/- SD) (min, max)]					

Follow-Up Completed					
Quarter 1 [(mean +/- SD) (min, max)]	n= xx.x +/- xx.x (xx,xx)				
Quarter 2 [(mean +/- SD) (min, max)]					
Quarter 3 [(mean +/- SD) (min, max)]					
Quarter 4 [(mean +/- SD) (min, max)]					
Follow-Up Not Done [(mean +/- SD) (min, max)]					

**Skindex-29, Functioning**

Baseline Completed [(mean +/- SD) (min, max)]	n= xx.x +/- xx.x (xx,xx)				
Baseline Not Done [(mean +/- SD) (min, max)]					

	n=	n=	n=	n=	n=
Follow-Up Completed					
Quarter 1 [(mean +/- SD) (min, max)]	xx.x +/- xx.x (xx,xx)				
Quarter 2 [(mean +/- SD) (min, max)]					
Quarter 3 [(mean +/- SD) (min, max)]					
Quarter 4 [(mean +/- SD) (min, max)]					
Follow-Up Not Done [(mean +/- SD) (min, max)]					

---

Patients can contribute multiple visits to a quarter during the follow-up period. These visits could be categorized as response or non-response for the same patient within a quarter.

Run Date: ddMMMyyyy

Date of Data Extraction: ddMMMyyyy

Helsinn Therapeutics (US), Inc.,  
 Protocol AC-079A501 (PROVe)

Table 17b. VAS for Pruritus and Skindex-29 by Response and by Valchlor Discontinuation (D/C) Early Termination

Responders a		Non-Responders	
D/C Due	D/C Due to Other	D/C Due	D/C Due to Other

Characteristic	All Patients	to AEs Patients	Reasons Patients	to AEs Patients	Reasons Patients
VAS for Pruritus					
Baseline Completed [(mean +/- SD) (min, max)]	n= xx.x +/- xx.x (xx,xx)				
Baseline Not Done [(mean +/- SD) (min, max)]					
Follow-Up Completed					
Quarter 1 [(mean +/- SD) (min, max)]	n= xx.x +/- xx.x (xx,xx)				
Quarter 2 [(mean +/- SD) (min, max)]					
Quarter 3 [(mean +/- SD) (min, max)]					
Quarter 4 [(mean +/- SD) (min, max)]					
Follow-Up Not Done [(mean +/- SD) (min, max)]					
Skindex-29 Emotions					
Baseline Completed [(mean +/- SD) (min, max)]	n= xx.x +/- xx.x (xx,xx)				
Baseline Not Done [(mean +/- SD) (min, max)]					
Follow-Up Completed					
Quarter 1 [(mean +/- SD) (min, max)]	n= xx.x +/- xx.x (xx,xx)				
Quarter 2 [(mean +/- SD) (min, max)]					
Quarter 3 [(mean +/- SD) (min, max)]					

Quarter 4 [(mean +/- SD) (min, max)]  
 Follow-Up Not Done [(mean +/- SD) (min, max)]

**Skindex-29 Symptoms**

Baseline Completed [(mean +/- SD) (min, max)]	n= xx.x +/- xx.x (xx,xx)				
Baseline Not Done [(mean +/- SD) (min, max)]					

Follow-Up Completed					
Quarter 1 [(mean +/- SD) (min, max)]	n= xx.x +/- xx.x (xx,xx)				
Quarter 2 [(mean +/- SD) (min, max)]					
Quarter 3 [(mean +/- SD) (min, max)]					
Quarter 4 [(mean +/- SD) (min, max)]					
Follow-Up Not Done [(mean +/- SD) (min, max)]					

**Skindex-29, Functioning**

Baseline Completed [(mean +/- SD) (min, max)]	n= xx.x +/- xx.x (xx,xx)				
Baseline Not Done [(mean +/- SD) (min, max)]					

Follow-Up Completed	n=	n=	n=	n=	n=
---------------------	----	----	----	----	----

Quarter 1 [(mean +/- SD) (min, max)]	xx.x +/- xx.x (xx,xx)				
Quarter 2 [(mean +/- SD) (min, max)]					
Quarter 3 [(mean +/- SD) (min, max)]					
Quarter 4 [(mean +/- SD) (min, max)]					
Follow-Up Not Done [(mean +/- SD) (min, max)]					

- 
- a. Patients can contribute multiple visits to a quarter. These visits could be categorized as response or non-response for the same patient within a quarter.

Run Date: ddMMMyyyy

Date of Data Extraction: ddMMMyyyy

Helsinn Therapeutics (US),  
 Inc., Protocol AC-079A501  
 (PROVe)

Table 18. Adverse Events

Characteristic	V+C+ Other	V+P+ Other	V+OB+ Other	V+ Other
	n=		n=	n=
Overall a	xx (xx.x)		xx (xx.x)	xx (xx.x)
System Organ Class 1				
Preferred Term A				
Preferred Term B	xx.x +/- xx.x		xx.x +/- xx.x	xx.x +/- xx.x
...				
System Organ Class 2				
Preferred Term C	xx (xx.x)		xx (xx.x)	xx (xx.x)
...				
...				

---

Note: Number of subjects and % of subjects are shown

a. Overall refers to any recorded AE, including AEs reported as ongoing at the time of enrollment

Run Date: ddMMMyyyy

Date of Data Extraction: ddMMMyyyy

Helsinn Therapeutics (US), Inc.,  
 Protocol AC-079A501 (PROVe)  
 Table 19. Serious Adverse Events

Characteristic	V+C+ Other	V+P+ Other	V+OB+ Other	V+ Other
	n= xx (xx.x)	n= xx (xx.x)	n= xx (xx.x)	n= xx (xx.x)
Overall a				
System Organ Class 1				
Preferred Term A				
Preferred Term B	xx.x +/- xx.x	xx.x +/- xx.x	xx.x +/- xx.x	xx.x +/- xx.x
...				
System Organ Class 2				
Preferred Term C	xx (xx.x)	xx (xx.x)	xx (xx.x)	xx (xx.x)
...				
...				

Note: Number of subjects and % of subjects are shown

a. Overall refers to any recorded AE, including AEs reported as ongoing at the time of enrollment

Run Date: ddMMMyyyy

Date of Data Extraction: ddMMMyyyy

Table 20. Continuous vs. Non-Continuous Exposure

Characteristic	Overall	Continuous Exposure (n=xx)	Non-Continuous Exposure (n=xx)
Total days of exposure, mean (SD)	xx.x (xx.x)	xx.x (xx.x)	xx.x (xx.x)
Days of longest continuous exposure, mean (SD)	xx.x (xx.x)	xx.x (xx.x)	xx.x (xx.x)

Helsinn Therapeutics (US), Inc.,  
 Protocol AC-079A501 (PROVe)

Table 21. Percent of patients with  $\geq 50\%$  reduction from baseline in % Body Surface Area of disease at 12 months ( $365 \pm 90$  days)

	IA and IB Staging	All Staged	All patients with and without Staging
	N=	N=	N=
V+C+Other			
V+P+Other			
V+OB+Other			
V+C+P+Other			
V+C+P			
V+Other			

Table 21a. Percent of patients with  $\geq 50\%$  reduction from baseline in % Body Surface Area of disease in 12 months – All Patients

Helsinn Therapeutics (US), Inc.,  
 Protocol AC-079A501 (PROVe)

Table 22. Percent of patients with  $\geq 50\%$  reduction from baseline in % Body Surface Area of disease at each visit preceding and following the 12 month visit, including months 1, 3, 6, 9, 12, 15, 18, 21 and 24  $\pm$  45 days.

	IA and IB Staging	All Staged	All patients with and without Staging
Month 1	N=	N=	N=
V+C+Other			
V+P+Other			
V+OB+Other			
V+C+P+Other			
V+C+P			
V+Other			
Month 3	N=	N=	N=
V+C+Other			
V+P+Other			
V+OB+Other			
V+C+P+Other			
V+C+P			
V+Other			
Month 6	N=	N=	N=
V+C+Other			
V+P+Other			
V+OB+Other			
V+C+P+Other			
V+C+P			
V+Other			
Month 9	N=	N=	N=
V+C+Other			
V+P+Other			
V+OB+Other			
V+C+P+Other			
V+C+P			
V+Other			
Month 12	N=	N=	N=
V+C+Other			
V+P+Other			
V+OB+Other			
V+C+P+Other			

V+C+P			
V+Other			
Month 15	N=	N=	N=
V+C+Other			
V+P+Other			
V+OB+Other			
V+C+P+Other			
V+C+P			
V+Other			
Month 18	N=	N=	N=
V+C+Other			
V+P+Other			
V+OB+Other			
V+C+P+Other			
V+C+P			
V+Other			
Month 21	N=	N=	N=
V+C+Other			
V+P+Other			
V+OB+Other			
V+C+P+Other			
V+C+P			
V+Other			
Month 24	N=	N=	N=
V+C+Other			
V+P+Other			
V+OB+Other			
V+C+P+Other			
V+C+P			
V+Other			

Helsinn Therapeutics (US), Inc.,  
 Protocol AC-079A501 (PROVe)

Table 23. Overall Response Rate 2 (ORR2) Percent of patients with  $\geq 50\%$  reduction from baseline in % Body Surface Area of disease for at least two consecutive visits

	Patients Contributing Data		
	IA and IB Staging	All Staged	All patients with and without Staging
	N=	N=	N=
V+C+Other			
V+P+Other			
V+OB+Other			
V+C+P+Other			
V+C+P			
V+Other			

Helsinn Therapeutics (US), Inc.,  
 Protocol AC-079A501 (PROVe)

Table 24. Overall Response Rate 4 (ORR4) Percent of patients with  $\geq 50\%$  reduction from baseline in % Body Surface Area of disease for at least four consecutive visits

	Patients Contributing Data		
	IA and IB Staging	All Staged	All patients with and without Staging
	N=	N=	N=
V+C+Other			
V+P+Other			
V+OB+Other			
V+C+P+Other			
V+C+P			
V+Other			

Helsinn Therapeutics (US), Inc.,  
 Protocol AC-079A501 (PROVe)

Table 25. Time to Next Treatment (TTNT)

	Patients Contributing Data		
	IA and IB Staging	All Staged	All patients with and without Staging
Median TTNT (mo)	N=	N=	N=
V+C+Other			
V+P+Other			
V+OB+Other			
V+C+P+Other			
V+C+P			
V+Other			
TTNT 95% CI (mo)	N=	N=	N=
V+C+Other			
V+P+Other			
V+OB+Other			
V+C+P+Other			
V+C+P			
V+Other			
6mo free from further treatment (%)	N=	N=	N=
V+C+Other			
V+P+Other			
V+OB+Other			
V+C+P+Other			
V+C+P			
V+Other			
1-y free from further treatment (%)	N=	N=	N=
V+C+Other			
V+P+Other			
V+OB+Other			
V+C+P+Other			
V+C+P			
V+Other			
18mo free from further treatment (%)	N=	N=	N=
V+C+Other			
V+P+Other			
V+OB+Other			
V+C+P+Other			
V+C+P			
V+Other			

Statistical Analysis Plan  
Valchlor PROVe  
November 2019  
Version Number: 3.0

2-y free from further treatment (%)	N=	N=	N=
V+C+Other			
V+P+Other			
V+OB+Other			
V+C+P+Other			
V+C+P			
V+Other			

Statistical Analysis Plan  
 Valchlor PROVe  
 November 2019  
 Version Number: 3.0

Helsinn Therapeutics (US), Inc.,  
 Protocol AC-079A501 (PROVe)

Table 26. Rates of on-study hospitalization

	Patients Contributing Data		
	IA and IB Staging	All Staged	All patients with and without Staging
	N=	N=	N=
V+C+Other			
V+P+Other			
V+OB+Other			
V+C+P+Other			
V+C+P			
V+Other			

Helsinn Therapeutics (US), Inc.,  
 Protocol AC-079A501 (PROVe)

Table 27a. Change from baseline at each timepoint in PRO questionnaires: Pruritis VAS

	Patients Contributing Data		
	IA and IB Staging	All Staged	All patients with and without Staging
Month 1	N=	N=	N=
V+C+Other			
V+P+Other			
V+OB+Other			
V+C+P+Other			
V+C+P			
V+Other			
Month 3	N=	N=	N=
V+C+Other			
V+P+Other			
V+OB+Other			
V+C+P+Other			
V+C+P			
V+Other			
Month 6	N=	N=	N=
V+C+Other			
V+P+Other			
V+OB+Other			
V+C+P+Other			
V+C+P			
V+Other			
Month 9	N=	N=	N=
V+C+Other			
V+P+Other			
V+OB+Other			
V+C+P+Other			
V+C+P			
V+Other			
Month 12	N=	N=	N=
V+C+Other			
V+P+Other			
V+OB+Other			
V+C+P+Other			

V+C+P			
V+Other			
Month 15	N=	N=	N=
V+C+Other			
V+P+Other			
V+OB+Other			
V+C+P+Other			
V+C+P			
V+Other			
Month 18	N=	N=	N=
V+C+Other			
V+P+Other			
V+OB+Other			
V+C+P+Other			
V+C+P			
V+Other			
Month 21	N=	N=	N=
V+C+Other			
V+P+Other			
V+OB+Other			
V+C+P+Other			
V+C+P			
V+Other			
Month 24	N=	N=	N=
V+C+Other			
V+P+Other			
V+OB+Other			
V+C+P+Other			
V+C+P			
V+Other			

Table 27b. Change from baseline at each timepoint in PRO questionnaires: SkinDex-29

Table 27c. Change from baseline at each timepoint in PRO questionnaires: MF/SS CTCL QOL instrument

Table 28. Other Treatments for MF-CTCL

Therapy	Prior to Mechlorethamine Treatment (N=289) (N/%)	During Mechlorethamine Treatment (N=289) (N/%)	Mean Treatment Duration During PROVe Study
Skin-directed therapy, n (%)	226 (78)	125 (43)	
Phototherapy	143 (49.5)	33 (11)	
UVB/Narrow Band-UVB			
PUVA/UVA-1			
ECP – Therakos (extracorporeal photopheresis)			
Radiation therapy (TSEB)	38 (13)	16 (5.5)	
Chemotherapy (topical) Name the 1 agent	4 (1)	1 (<1)	
Corticosteroids (topical)	165 (57)	88 (30)	
See full list below for reference only			
Retinoid (topical)	39 (13.5)	9 (3)	
Bexarotene			
tazarotene			
adapalene			
Imiquimod (topical)	18 (6)	7 (2)	
Systemic therapy, n (%)	83 (29)	47 (16)	
Chemotherapy (systemic)	18 (6)	11 (4)	
methotrexate			
CHOP (cyclophosphamide + vincristine + Adriamycin + prednisone)			
Liposomal doxorubicin			
gemcitabine			
pentostatin			
Monoclonal Antibodies			
Brentuximab			
Alemtuzamab			
Mogamulizumab			

Interferon			
Retinoids (systemic)	59 (20)	36 (12.5)	
Bexarotene			
HDAC Inhibitors	20 (7)	6 (2)	
Vorinostat			
Remetinostat			
Romidepsin			
Panobinostat			

Listing 1: Serious Adverse Events

Patient ID, AE Date, System Organ Class, Preferred Term, Verbatim Term, Completed/Discontinued, Reason for Discontinuation

Listing 2: Serious Adverse Events Resulting in Death

Patient ID, AE Date, System Organ Class, Preferred Term, Verbatim Term

Listing 3: Adverse Events

Patient ID, AE Date, System Organ Class, Preferred Term, Verbatim Term

Listing 4: Pregnancy

Patient ID, Age, Sex/Gender, Positive Pregnancy Confirmation

Listing 5: Secondary Exposures

Patient ID, Age, Sex/Gender, Positive Secondary Exposure

Listing 6: Patient Disposition

Patient ID, D/C Date, Reason for D/C

Listing 7: Demographic and Baseline Characteristics by Subject and Treatment Group

Patient ID, Age, Gender, Race, MF Stage, Date of First Diag, CAILS, SWAT, %BSA

Listing 8: Efficacy Data (CAILS, SWAT Scores and % Body Surface Area with Response Assessment) by Subject and Treatment Group

Patient ID, Age/Gender/Race MF Stage, Visit Dt, CAILS, CAILS Change, CAILS Response, SWAT, SWAT Change, SWAT Response, %BSA, %BSA Change, %BSA Response

Listing 9: Subjects Who Reported Adverse Events

Patient ID, Age/Gender/Race, MF Stage, AE PT, Onset Dt, Duration, Serious, Rel to Med, Intensity, Action Taken
